Definition of primary outcome/endpoint: RT-related grade ≥ 4 toxicity will be determined on a case-by-case basis by the study group, taking into consideration the region treated with SBRT, timing of the toxicity, and the nature of the toxicity. Toxicities will be graded as per CTCAE v4.0 criteria.

Definition of secondary outcomes/endpoints: LeC will be defined as absence of clinical or radiographic progression per RECIST criteria. PFS will be defined as progression in the treated lesion, organ in which the treated lesion is present, distant failure, or death from any cause.

Analytic plan for primary objective: Rates of RT-related grade ≥ 4 toxicity will be recorded, time to RT-related grade ≥ 4 toxicity will be recorded, and freedom from RT-related grade ≥ 4 toxicity will be determined using the Kaplan-Meier method.

Analytic plan for secondary objectives: LeC and PFS will be estimated at 1 year using the Kaplan-Meier method.

Sample size justification: A sample size of 25 patients will be needed to assess the safety and appropriateness of this method, identify the optimal candidates, and optimal SBRT fractionation/dose for different clinical scenarios.

TABLE OF CONTENTS

	Page
SCHEMA	i
1. OBJECTIVES	1
1.1 Primary Objectives	1
1.2 Secondary Objectives	1
2. BACKGROUND	1
2.1 Metastatic Renal Cell Carcinoma	1
2.2 Oligometastasis	1
2.3 Stereotactic Body Radiotherapy in Oligometastasis	2
2.4 Rationale for current study	3
2.4.1 Rationale for Secondary Objectives	4
3. PATIENT SELECTION	4
3.1 Eligibility Criteria	4
3.2 Exclusion Criteria	5
3.3 Inclusion of Women and Minorities	6
4. REGISTRATION PROCEDURES	6
4.1 Patient Recruitment	6
4.2 Patient Renumeration	6
5. TREATMENT PLAN	6
5.1 Study Design	6
5.2 Definition of Grade ≥ 4 RT-related Toxicity	6
5.3 General Concomitant Medication and Supportive Care Guidelines	7
5.4 Duration of Therapy	7
5.5 Duration of Follow Up	7
5.6 Criteria for Removal from Study	7
6. RADIATION THERAPY	7
6.1 Simulation	7
6.2 Premedications	8
6.3 Target Volumes	8
6.4 Treatment Planning	8
6.5 Dose Specifications	8
6.6 Critical Structures	9
6.7 RT Treatment	13
6.8 Radiotherapy Adverse Events	13
7. RISKS AND BENEFITS	13
7.1 Radiotherapy Adverse Events	13
8. Adverse Event Reporting	15
9. Data Safety Monitoring	16
10. STUDY CALENDAR	16
11. MEASUREMENT OF EFFECT	17
11.1 Antitumor Effect and Endpoints	17
11.2 Dosimetric description of delivery of Radiotherapy	18
12. STATISTICAL CONSIDERATIONS	19
12.1 Study Design/Endpoints	19

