6.5 Dose Specifications

Doses will be prescribed to the PTV. The PTV may be covered by a lower isodose line than usually used in conventional radiotherapy planning, ranging from 60-100%. Ideally, the prescription dose will cover $>90\%$ of the GTV ($V_{100} \text{ GTV} > 90\%$, and $V_{95} \text{ PTV} > 90\%$). Hot spots within the PTV are allowed, unless the PTV also overlaps an organ at risk. A lower coverage goal will be acceptable if necessary to meet normal tissue constraints, which will be assigned priority over tumor coverage.

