11.1.4 Response Criteria

11.1.4.1 Evaluation of Target Lesions will occur to determine lesion control at each CT scan evaluation. Local control will be defined as the lack of progressive disease based on the criteria below:

Complete Response (CR):	Disappearance of target lesion
Partial Response (PR):	At least a 30% decrease in the sum of the longest diameter (LD) of target lesion, taking as reference the baseline sum LD
Progressive Disease (PD):	At least a 20% increase in the sum of the LD of target lesion, taking as reference the smallest sum LD recorded since the treatment
Stable Disease (SD):	Neither sufficient shrinkage to qualify for PR nor sufficient increase to qualify for PD, taking as reference the smallest sum LD since the treatment started

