11.1.5 Endpoint Definitions

Duration of treated lesion control

Duration of time from start of treatment to the time of local progression at each treated lesion. Local progression is defined as any progressive disease as judged by RECIST criteria of treated lesions

Organ-specific control

Duration of time from start of treatment to the time of development of a new lesion on imaging within an organ in which a lesion was treated with SBRT.

Progression-free survival

Duration of time from start of treatment to time of progression. Progression is defined as any new sites of disease on imaging or any progressive disease by RECIST criteria at initially treated sites of disease (within 80% isodose line).

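### Section 11.1.5 limits treated-site PFS events by an isodose qualifier and omits death, in conflict with treated lesion control and with the synopsis PFS

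*Combined protocol and SAP*

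**What the plan says.** The documents define PFS twice and treated lesion control once in terms that bear on this point.

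- **PFS, section 11.1.5.** It runs from start of treatment. "Progression is defined as any new sites of disease on imaging", or as "any progressive disease by RECIST criteria at initially treated sites of disease (within 80% isodose line"). Death is not listed.
- **Treated lesion control, section 11.1.5.** "Local progression is defined as any progressive disease as judged by RECIST criteria of treated lesions". There is no isodose limit.
- **PFS, synopsis (Statistical Methods).** "PFS will be defined as progression in the treated lesion, organ in which the treated lesion is present, distant failure, or death from any cause". There is no isodose limit, and death counts.
- **Progressive disease, section 11.1.4.** "At least a 20% increase in the sum of the LD of target lesion", measured from the smallest value since treatment. This is a diameter criterion with no dose-region component.
- **Which definition is used.** Section 12.5 says that progression-free survival, with the other durations, will be calculated for each patient using the definitions in 11.1.5.
- **Dose coverage, section 6.5.** "The PTV may be covered by a lower isodose line than usually used in conventional radiotherapy planning, ranging from 60-100" percent. Also: "A lower coverage goal will be acceptable if necessary to meet normal tissue constraints, which will be assigned priority over tumor coverage".

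No section says whether the 80% line is a percentage of maximum or of prescription dose, or how a change in diameter is assigned to one side of an isodose line.

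**The concern.** PFS should include every progression that ends lesion control. Under 11.1.5 taken literally it does not: a single scan could end lesion control for a treated lesion while the patient remains progression-free. The new-site clause does not close this gap. Section 11.1.2 treats later-appearing lesions as separate from the original targets, and growth continuous with a target is not a new lesion.

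The error runs one way. Compared with the same definition without the qualifier, a patient's PFS time can only stay the same or lengthen. Leaving out death acts in the same direction, because a patient who dies without documented progression has no event under 11.1.5.

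PFS is a named secondary endpoint, to be estimated at 1 year by Kaplan-Meier. Section 2.4 says the pilot's data should help size later trials, so an optimistic PFS would be carried forward.

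**Working it through.** The plan states no PFS rate, power or precision, so there is no figure to reproduce. The check sets the definitions side by side and then asks where the 80% line lies.

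**Step 1. Event coding under each definition (11.1.5 read literally)**

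| Observation | Lesion control, 11.1.5 | PFS, 11.1.5 | PFS, synopsis |
|---|---|---|---|
| Treated lesion meets progressive disease, growth within the 80% line | event | event | event |
| Treated lesion meets progressive disease, contiguous growth outside the 80% line | event | no event | event |
| Separate new lesion | no event | event | event |
| Death without documented progression | not listed | not listed | event |

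The second and fourth rows are the conflicts. Because 12.5 points to 11.1.5, the synopsis wording does not resolve either one.

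**Step 2. The 80% line as a percentage of maximum dose**

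Inputs: covering isodose i from 60% to 100% (6.5) and the preferred 50 Gy in 5 fractions (6.5.1), used for illustration only. If the prescription is set at isodose i of maximum, maximum dose = prescription / i, and 80% of maximum = (0.80 / i) × prescription.

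| Covering isodose i | 0.80 / i | Dose at the 80% line if prescription is 50 Gy |
|---|---|---|
| 60% | 133% | 66.7 Gy |
| 70% | 114% | 57.1 Gy |
| 80% | 100% | 50.0 Gy |
| 90% | 89% | 44.4 Gy |
| 100% | 80% | 40.0 Gy |

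Whenever i is below 80%, the 80% line lies inside the prescription surface, so part of the PTV is outside it. Section 6.4.5 agrees: it keeps any dose above 110% within the PTV, and both 133% and 114% exceed 110%.

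**Step 3. The 80% line as a percentage of prescription dose**

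The line is then 0.80 × 50 = 40 Gy, or 0.80 × 40 = 32 Gy for the 8 Gy × 5 alternative, whatever the covering isodose. It lies outside the prescription surface. Where the 6.5 goal of V95 above 90% for the PTV is met, more than 90% of the PTV is inside it. Two gaps remain:

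- growth that extends past the line;
- target regions where coverage was reduced to meet constraints.

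As an example of the second, Table 1 allows less than 0.5 cc of duodenum to reach 30 Gy, and 30 Gy is below both 32 and 40 Gy. PTV overlapping the duodenum beyond that volume would therefore have to lie outside the line at either prescription. This assumes that the prescription itself is not reduced to 30 / 0.80 = 37.5 Gy or less, which section 6 also leaves open.

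**Step 4. Scale**

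With 25 patients and no censoring before 1 year, one patient whose event is lost or moved past 1 year changes the estimate by 1/25 = 4 percentage points. The documents give no basis for predicting how many patients this would be.

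**The case against.** The strongest reply is that the parenthesis only describes what a treated site is. Disease in that region is then judged by RECIST, and disease elsewhere is a new site, which counts anyway. On that reading a lesion that straddles the line and meets the diameter criterion is still progression at a treated site, and almost nothing is lost. This is a fair reading and cannot be excluded. Against it, 11.1.2 already defines target lesions without any isodose, so the phrase would be redundant, and contiguous growth beyond the line would still be left to each reader's judgment.

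A reader might also set 60% against 80% and infer that a large part of the target is necessarily outside the PFS definition. The documents do not support that. The comparison works only if both percentages refer to maximum dose. The 110% limit in 6.4.5 cannot be a percentage of maximum, and V100 and V95 in 6.5 are prescription coverage goals. Nor can the gap be converted into a fraction of target volume and read as bias. The distance between the lines is not given, the PTV includes margins around the visible lesion (6.3.1), and volume outside a line is not a count of missed events.

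Finally, PFS here is descriptive, 12.5 plans no formal testing, and lesion control is reported separately without the limit, so these failures would still be visible. All of that stands, and it limits the weight of the point.

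**Conclusion.** The point holds as a conflict between definitions. The definition that 12.5 makes operative carries an isodose qualifier found in neither lesion control nor the synopsis PFS, and it omits death, which the synopsis includes. That treated-lesion growth can escape PFS depends on reading the parenthesis literally; it is not certain that anyone would code events that way. If they did, the bias would be upward only.

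Its size cannot be derived. It could be appreciable if the 80% refers to maximum dose and low covering isodoses are used, and small if it refers to prescription dose. It would be wrong to conclude that the whole plan restricts PFS in this way, since the synopsis does not, or that a known share of local failures will be missed.

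The effect is confined to a descriptive secondary endpoint. The primary toxicity endpoint, the 25-patient sample size and the stopping rule do not depend on it. The correction should still be made, because it is nearly free and removes a one-directional ambiguity.

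**What to change.** Use one PFS definition in the synopsis and in 11.1.5: time from start of treatment to the first of RECIST progression of any treated lesion, any new site of disease, or death from any cause. Delete the isodose qualifier from PFS. Deleting it alone is not enough, because 11.1.5 would still omit death and would still differ from the synopsis.

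If the 80% line is useful, keep it only to classify failures as in-field or marginal in the patterns-of-failure description, and state whether it is a percentage of maximum or of prescription dose.

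The cost is a short text change in two places. Follow-up imaging is already scheduled, and 12.5 already plans to calculate overall survival, so no new data are needed. The downside is that reported PFS may be slightly lower.

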11.2 Dosimetric description of delivery of Radiotherapy

Radiation plans, target volumes, and DVHs will be reviewed to assess for acceptable doses based on site and normal tissue toxicity dose constraints. Descriptive statistics will be calculated for each dose cohort to characterize these dosimetric parameters. The relationship between grade of toxicity and dose parameters will also be described.

12. STATISTICAL CONSIDERATIONS

12.1 Study Design/Endpoints

This is a pilot study of the use of 5-fraction SBRT for oligometastatic RCC. Patients enrolled in the study will be treated with SBRT to all sites of disease. Enrollment will proceed according to a sequential toxicity monitoring schema [69] to test the null hypothesis of a $\pi_0=5\%$ grade 4 toxicity rate against an upper acceptable boundary of a $\pi_1=20\%$ grade 4 toxicity rate. Trial enrollment will be halted if there are two grade 4 events within the first 2 patients, if there are three events within the first 14 patients, or if there are four events within the first 25 patients. The treatment will be considered successful if there are less than four events in 25 patients, i.e., $<16\%$ observed toxicities. This design has approximately 80% power (78.8%) to declare the treatment too toxic if the true grade 4 toxicity rate is $\pi_1=20\%$.

Patients will be followed for a total of one year after completion of the trial per protocol. Patients may be treated with off-protocol systemic therapy no earlier than 2 weeks after completion of RT. The primary endpoint is the rate of grade 4 RT-related toxicity with this treatment approach. Secondary endpoints include determining the toxicity profile of 5-fraction SBRT, determining the feasibility of 5-fraction SBRT based on normal tissue dosimetric constraints based on the organ site of involvement, describing the LeC, PFS, and patterns of failure of this approach, as well as to explore the feasibility of accrual and the adequacy of the eligibility criteria of this approach.

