TITLE: A PILOT STUDY OF STEREOTACTIC BODY RADIOTHERAPY (SBRT) IN OLIGOMETASTATIC RENAL CELL CARCINOMA

Principal Investigator: [name].
Department of Radiation and Cellular Oncology
University of Chicago Medical Center
[name]
[name]
[contact]
[contact]
[contact]

Sub-Investigators:

Radiation Oncology
[name] PHD
[name]
[name]

Urology
[name]
[name]
[name]

Medical Oncology
[name]
[name]
[name]
[name]

Biostatistics
[name]

Research and Nursing Support
[name]
[name]

Funding: Internally funded through the Department of Radiation and Cellular Oncology

Sponsor: [name]./University of Chicago

Intervention: Stereotactic Body Radiotherapy to all sites of disease

Protocol Version: 2.0

Protocol Version Date: 08.05.19

STUDY SUMMARY SCHEMA

Patient population:

- Histologically or cytologically diagnosed renal cell carcinoma (any histologic subtype)
- No systemic therapy or radiation therapy within 1 month prior to enrollment
 - No prior bevacizumab
- ECOG performance score 0-2 and ≥ 3 month life expectancy
- 1-5 sites of metastatic (or recurrent) disease, each ≤ 6 cm and amenable to SBRT
 - Up to 3 brain metastases may be included

Treatment:

- 25 patients will be enrolled and treated according to protocol guidelines for SBRT
- Brain metastases must be addressed prior to enrollment
- Day1 : Begin SBRT to all involved sites, 5 fractions on non-consecutive days
- Enrollment halted if there are two grade 4 toxicities within the first 2 patients, three within the first 14 patients, or 4 within the first 25 patients

Follow-up:

- Clinical follow-up to assess CTC toxicity and disease control, monthly up to 3 months, then q3 months up to 1 year
- CT chest/abdomen/pelvis q3 months up to 1 year
- Off protocol therapy at clinician discretion but no earlier than 4 weeks after start of SBRT

Required Sample Size: 25 patients would be required

Study Center: University of Chicago Medical Center, Chicago, IL

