Concept and Rationale: Patients with metastatic renal cell carcinoma (RCC) have a poor prognosis with median survival between 6-15 months, as few patients have a lasting response to cytokine therapy or targeted agent therapy. However, not all patients present with widely metastatic disease. There may be a select group of patients with “oligometastatic” disease—a limited number of metastatic lesions that can be treated with curative intent using aggressive local and systemic therapy. Randomized studies suggest a benefit of cytoreductive surgery in the setting of cytokine therapy, and retrospective series suggest an improvement in survival with metastasectomy. These studies argue that aggressive local therapy to all known sites of disease can yield benefit in the properly selected patient.

However, not all lesions are amenable to surgical resection, and surgery can be associated with significant morbidity. Stereotactic Body Radiotherapy (SBRT) is a method of treatment which directs ablative doses of radiotherapy to the target lesion while limiting radiation to surrounding structures. There is an increasing body of evidence supporting a role for SBRT in oligometastatic cancers throughout the body. A prior Phase I trial at the University of Chicago suggested that a 3-fraction regimen is tolerable in oligometastatic cancer. However, this study included a heterogeneous cohort of patients with multiple primary malignancy types; only 13% of the patients in the trial had RCC. Furthermore, variable radiation doses were prescribed to different sites, complicating the applicability of findings to the clinical setting. Conclusions are therefore more difficult to make regarding the tolerability of SBRT in RCC.

We hypothesize that 5-fraction SBRT with a more uniform dose approach (by having a preferred SBRT dose that is similar for all sites of involvement) in the management of oligometastatic RCC is feasible, not associated with excess toxicity, and can be safely delivered prior to systemic therapy. Information gathered from this study will contribute towards the development of a larger, phase II Chicago consortium study.

Primary Objective: To establish that patients can be treated with 5-fraction SBRT to all sites of metastatic disease with a low (<16%) rate of severe (grade 4) toxicity.

Secondary Objectives:

1. To determine the toxicity profile of SBRT.

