2. To determine the feasibility of delivering 5-fraction SBRT per protocol based on proposed normal tissue constraints in a variety of organ sites. (i.e., the ability to treat >80% of enrolled patients according to protocol guidelines).
3. To describe treated lesion control (LeC), progression free survival (PFS), and patterns of failure.
4. To determine the feasibility of accrual and adequacy of eligibility criteria by defining the proportion of eligible cases of metastatic RCC presented at the weekly multidisciplinary genitourinary conference at the University of Chicago Medical Center.
5. To make a preliminary evaluation regarding potential biomarkers in patient serum which may be assessed in a follow-up study (e.g. genetic or immunologic biomarkers).

Study Design: This is a single-armed pilot study to estimate the rate of CTCAE v4.0 grade ≥ 4 RT-related toxicity of 5-fraction SBRT in patients with oligometastatic RCC. Eligible patients must have histologically or cytologically diagnosed RCC with 1-5 sites of metastases, including up to 3 brain metastases. Patients may present with metastatic disease, or have previously treated primary disease with metastatic recurrence. All sites of metastasis must be ≤ 6 cm, and patients with recurrent/unresected primary tumors are eligible as long as said tumor is ≤ 10 cm and there is a plan to treat the primary tumor with a local therapy. Patients may not have had any oncologic therapy within 1 month prior to enrollment, no prior history of bevacizumab, and any brain metastases must be addressed with surgery and/or radiotherapy prior to enrollment. Patients will be treated with SBRT (preferred dose 50 Gy/5 fractions) to all radiographic sites of gross disease, including the primary if it can not be addressed with non-radiotherapeutic local therapy. Patients can thereafter begin off-protocol systemic therapy per medical oncology discretion, but any therapy will occur no earlier than 2 weeks after completion of RT.

The first 10 patients enrolled on the study will be considered the "initial cohort." If ≥ 3 of these patients have a CTCAE v4.0 grade ≥ 4 RT-related toxicity, enrollment will be discontinued and the trial stopped, otherwise 5 additional patients will be accrued. Study investigators will determine whether treatment related toxicities are RT-related or non-RT-related.

Statistical Methods:

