5. TREATMENT PLAN

5.1 Study Design

This is a pilot study of the use of SBRT to all sites of disease for patients with oligometastatic RCC. Patients may receive off-protocol systemic therapy per medical oncologist discretion no earlier than 4 weeks after starting SBRT. While there are no restrictions on systemic therapy following SBRT, caution is advised on the use of bevacizumab given prior case reports demonstrating the possibility of heightened toxicity when this agent is used in the setting of SBRT. Limited or symptomatic recurrences can also be treated with radiation therapy (either SBRT or conventional therapy) at the clinician's discretion.

Enrollment will proceed according to a sequential toxicity monitoring schema to test the null hypothesis of a $\pi_0=5\%$ grade 4 toxicity rate against an upper acceptable boundary of a $\pi_1=20\%$ grade 4 toxicity rate. Trial enrollment will be halted if there are two grade 4 events within the first 2 patients, if there are three events within the first 14 patients, or if there are four events within the first 25 patients. The treatment will be considered successful if there are less than four events in 25 evaluable patients (<16%).

Treatment will be administered on an outpatient basis. The details of planning and administration of radiotherapy are discussed in detail in section 6. Reported adverse events and potential risks for SBRT are described in Section 8. Appropriate dose modifications for SBRT are described in Section 6. No investigational or commercial agents or therapies other than those described below may be administered with the intent to treat the patient's malignancy.

The pilot study will be considered successful if 25 patients are accrued, with less than 4 having Grade 4+ toxicity events after SBRT.

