12.4 Analysis of the Primary Endpoint

The primary endpoint is the rate of grade ≥ 4 RT-related toxicity with this treatment approach. RT-related toxicity will be recorded as specified in the study calendar (section 10). All toxicity will be determined to be RT-related or non-RT-related by the study committee.

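### The rules that decide the primary endpoint disagree on what is counted (grade 4 events, or patients with grade 4 or worse), and the synopsis carries a halting rule that ends at 15 patients, not 25

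*Combined protocol and SAP*

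**What the plan says.** The places that define or use the primary count, all in the current text (the synopsis is the part before the table of contents):

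- **Primary objective** (synopsis and Section 1.1): treatment "with a low (<16%) rate of severe (grade 4) toxicity".
- **Study Summary Schema**: "Enrollment halted if there are two grade 4 toxicities within the first 2 patients", then three within 14 or four within 25. Sections 5.1 and 12.1 repeat this boundary.
- **Section 12.1, success rule**: "The treatment will be considered successful if there are less than four events in 25 patients". The first success sentence of Section 5.1 is the same except that it says evaluable patients.
- **Section 5.1, last sentence**: success if 25 are accrued "with less than 4 having Grade 4+ toxicity events after SBRT".
- **Section 12.1, endpoint**: "The primary endpoint is the rate of grade 4 RT-related toxicity with this treatment approach".
- **Section 12.4, endpoint**: "The primary endpoint is the rate of grade ≥ 4 RT-related toxicity with this treatment approach". The synopsis definition of the primary endpoint uses the same threshold.
- **Synopsis, Study Design**, on the first 10 patients: "If ≥ 3 of these patients have a CTCAE v4.0 grade ≥ 4 RT-related toxicity, enrollment will be discontinued and the trial stopped". Failing that, the trial adds five more, 15 in all.
- **Sample size**: 25 in the schema, the synopsis sample size justification and Section 12.2.

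On timing, Section 5.2 sets a 90-day acute period from the first fraction and lets later grade ≥ 4 toxicity change design and accrual at the investigator's discretion. Section 7.1 follows late reactions to 12 months. Section 12.5 describes toxicities at 3 to 12 months. The synopsis plans a Kaplan-Meier analysis of RT-related grade ≥ 4 toxicity with no cut-off.

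**The concern.** The trial has one formal decision, and it turns on whether a count reaches four. Three features of that count are not fixed.

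First, grade and unit. Grade 4 is not the same as grade 4 or worse, because CTCAE grade 5 is death. Events are not the same as patients, because one patient can have several. Section 5.1 contradicts itself on both, and its last sentence contradicts 12.1.

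Second, the halting rule. The synopsis version leads to a trial of 15, which cannot produce a verdict on 25 and is not the design whose power is quoted.

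Third, and minor, the rule sentences do not repeat that the toxicity must be RT-related, and no sentence says whether toxicity after 90 days enters the count of four in 25.

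At stake is whether two people applying the same document to the same 25 patients reach the same verdict.

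**Working it through.** **Inputs.** From Section 12.1: π0 = 5%, π1 = 20%; halt at 2 events by patient 2, 3 by patient 14, 4 by patient 25; stated power 78.8%. From the synopsis: halt at 3 or more of the first 10, otherwise 5 more. Each patient is scored 0 or 1 with probability p.

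**1. Reproduce the stated power.** Halting happens if four or more of 25 patients are affected, or if an earlier boundary is crossed with fewer than four in total:

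P(halt) = P(X₂₅ ≥ 4) + C(14,3)p³(1−p)²² + p²(1−p)²³ + 11p³(1−p)²²

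The added terms are: exactly three affected, all within the first 14; only the first two patients affected; the first two plus one of the 11 patients after patient 14.

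- p = 0.20: 0.7660 + 0.0215 + 0.0002 + 0.0006 = 0.7884 (78.84%, against 78.8% stated).
- p = 0.05: 0.0341 + 0.0147 + 0.0008 + 0.0004 = 0.0500.

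The figure is right, and it comes from one yes/no outcome per patient. A patient-level count also fits the plan's own percentage, since 4/25 = 16%.

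**2. Can the verdict flip on grade alone?** Take three patients with RT-related grade 4 toxicity (not both of the first two, and the third after patient 14) and one patient who dies of RT-related toxicity.

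| Rule as written | Count | Result |
|---|---|---|
| 12.1, grade 4 events | 3/25 = 12%, no boundary crossed | successful |
| 5.1 last sentence, patients with grade 4 or worse | 4/25 = 16% | not successful |

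No assumed rate is needed. How often this occurs depends on the share of affected patients with grade 5 only, which the documents do not give. With an assumed 5% or 10%, the literal grade 4 rule reports success although at least four of 25 had grade ≥ 4 in 3.3% or 7.1% of trials at a true 20%, and in 0.4% or 0.8% at 5%.

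**3. Does events versus patients matter?** Suppose an assumed 10%, 25% or 50% of affected patients have a second counted event. Counting events then halts in 9.0%, 14.6% or 22.9% of trials at p = 0.05 (against 5.0%), and in 82.4%, 86.8% or 91.8% at p = 0.20 (against 78.8%). These shares are illustrative.

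**4. Compare the two halting rules over the same patients.** Through patient 10, the 12.1 boundary halts if three or more are affected, or if the first two are affected and no others:

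P(halt by 10) = P(X₁₀ ≥ 3) + p²(1−p)⁸

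| True rate | Synopsis rule, P(X₁₀ ≥ 3) | 12.1 boundary by patient 10 |
|---|---|---|
| 20% | 32.2% | 32.2% + 0.7% = 32.9% |
| 5% | 1.15% | 1.15% + 0.17% = 1.3% |

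The rules nearly coincide up to patient 10. They part afterwards: the synopsis states no further toxicity boundary and stops at 10 + 5 = 15, while 12.1 monitors to 25. At 15 patients neither the verdict on fewer than four in 25 nor the 78.8% applies.

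**The case against.** The strongest reply is that the intent is plain. The title of Section 5.2, the last sentence of 5.1, Sections 12.4 and 12.5 and the synopsis endpoint definition all point to grade ≥ 4. The 78.8% and the 16% fit a patient-level count, and no team would leave a treatment-related death out of a toxicity count. The synopsis rule stands alone against the schema, 5.1, 12.1 and 12.2, and may be leftover text.

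Most of this stands as a reading of intent, and it limits the severity. It does not remove the conflict. The operative sentences in 12.1 say otherwise, nothing states which text governs, and the synopsis gives a current stopping instruction.

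Some stronger readings are tempting but not supported:

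- *That the 78.8% is wrong.* It reproduces exactly.
- *That the synopsis rule is far weaker, 32.2% against 78.8%.* That sets a look at 10 patients against a boundary running to 25. Over the same 10 patients the figures are 32.2% and 32.9%.
- *That the rules deliberately count toxicity unrelated to RT.* The endpoint sentences in 12.1 and 12.4, and the committee classification in 5.2, 12.4 and 12.5, make RT-related the natural reading. The omission from the rule sentences is a wording gap.
- *That late toxicity is ignored.* Sections 5.2, 7.1 and 12.5 record it and allow action on it. What is missing is whether it enters the count of four.

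**Conclusion.** The inconsistency is real and should be fixed; the design calculation is sound. The same outcomes can be 12% and successful under 12.1, or 16% and not successful under the last sentence of 5.1. That result needs no assumption beyond reading each sentence as written. How often it would happen rests on assumed grade 5 shares and is small: 7.1% or less in the cases shown.

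The synopsis halting rule conflicts with the other places on what follows patient 10 and on whether the trial has 15 or 25 patients. The quoted power belongs only to the 12.1 boundary with 25 patients, each scored once. Attribution in the rule sentences and the time window are lesser points of the same kind. A reader might infer from the wording that the trial means to exclude RT-related deaths from its verdict; the grade ≥ 4 definitions elsewhere do not support that.

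**What to change.** Reconcile the Study Summary Schema; the synopsis (primary objective, study design, primary endpoint definition and its analysis); and Sections 1.1, 5.1 (both success sentences), 5.2, 7.1, 12.1, 12.4 and 12.5 to one counted outcome built from the plan's own terms: a patient with at least one RT-related CTCAE v4.0 toxicity of grade 4 or 5, as classified by the study committee, each patient counted once.

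State one window from the first fraction, say that π0 and π1 are rates for that window, and say whether late toxicity enters the halting count. Make the success statement when the window has closed for all 25 patients.

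Reconcile the synopsis halting rule and its 15 patients with the schema and Sections 5.1, 12.1 and 12.2. Which rule applies is for the sponsor.

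Cost: wording changes, and a later success statement if the window is longer than 90 days. If the 12.1 boundary and 25 patients are kept, 78.8% stands; otherwise the power must be restated for the rule chosen.
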